				400 mg QD	xxxx	ddMMMyyyy / hh:mm	x.x	xx	x.x to x.x	
					xxxx	ddMMMyyyy / hh:mm	x.x	xx	x.x to x.x	H
					xxxx	ddMMMyyyy / hh:mm	x.x	xx	x.x to x.x	
			...etc..							

F=Female; M=Male

Abnormal results are highlighted in yellow

Program: <program name (date, time)>, Path: <path>

Programming note: This listing excludes patients/parameters with normal results for all visits. Abnormal results and the Low/High flag will be highlighted in yellow.

Mock shells for Listing B.16.2.8.1 and Listing B.16.2.8.2 will be used for the following listings:

Listing B.16.2.8.3	Coagulation Results (Safety Population)
Listing B.16.2.8.4	Coagulation Results – Patients with Abnormal Results (Safety Population)
Listing B.16.2.8.5	Serum Chemistry Results (Safety Population)
Listing B.16.2.8.6	Serum Chemistry Results – Patients with Abnormal Results (Safety Population)
Listing B.16.2.8.7	Urinalysis Results (Safety Population)
Listing B.16.2.8.8	Urinalysis Results – Patients with Abnormal Results (Safety Population)
Listing B.16.2.8.9	Drug Induced Liver Injury (DILI) Test Results (Safety Population)
Listing B.16.2.8.10	Drug Induced Liver Injury (DILI) Test Results – Patients with Abnormal Results (Safety Population)

Listing B.16.2.8.11 Anti-DSG Antibodies Results (ITT Population)

Starting Dose	Patient ID	Age/ Gender	Visit	Current PRN Dose	Was the sample collected ?	Collection Date (ddMMMyyyy)	Collection Time (hh:mm 24h)	Lab Test	Result (unit)
400 mg QD	xxxxxxx	xx/F	xxx	400 mg QD	Yes	ddMMMyyyy	Hh:mm	Anti-DSG 1 Anti-DSG 3	xxx unit Xxx unit
...etc..									

F=Female; M=Male

Program: <program name (date, time)>, Path: <path>

Listing B.16.2.8.12 PK and BTK Sample Collection (ITT Population)

Starting Dose	Patient ID	Age/ Gender	Visit	Current PRN Dose	Was the sample collected?	Collection Date (ddMMMyyyy)	Collection Timepoint	Collection Time (hh:mm 24h)	Was PK sample performed for this visit?	Date of most recent prior dose received (ddMMMyyyy)	Time of most recent prior dose received (Hh:mm 24h)
400 mg QD	xxxxxxx	xx/F	xxx	400 mg QD	Yes	ddMMMyyyy	xxx	Hh:mm	Yes	ddMMMyyyy	Hh:mm
...etc..											

F=Female; M=Male

Program: <program name (date, time)>, Path: <path>

Listing B.16.2.8.13 Vital Signs and Body Weight (Safety Population)

Startin g Dose	Patient ID	Age/ Gender	Parameter	Current PRN Dose	Visit	Date / Time (ddMMMyyyy / hh:mm 24 hr)	Result	Normal Range	Low or High
400 mg QD	xxxxxxx	xx/F	SBP (mmHg)	---	xxxx	ddMMMyyyy / hh:mm	x.x	90 to 140	
				400 mg QD	xxxx	ddMMMyyyy / hh:mm	x.x	90 to 140	L
					xxxx	ddMMMyyyy / hh:mm	x.x	90 to 140	
					xxxx	ddMMMyyyy / hh:mm	x.x	90 to 140	
				400 mg QD	xxxx	ddMMMyyyy / hh:mm	x.x	90 to 140	
					xxxx	ddMMMyyyy / hh:mm	x.x	90 to 140	H
					xxxx	ddMMMyyyy / hh:mm	x.x	90 to 140	
					xxxx	ddMMMyyyy / hh:mm	x.x	90 to 140	
				...etc..					

F=Female; M=Male

Low or High results are highlighted in yellow.

Program: <program name (date, time)>, Path: <path>

Listing B.16.2.8.14 Vital Signs – Blood Pressure and Pulse – Patient with Abnormal Results (Safety Population)

Startin g Dose	Patient ID	Age/ Gender	Parameter	Current PRN Dose	Visit	Date / Time (ddMMMyyyy / hh:mm 24 hr)	Result	Normal Range	Low or High
400 mg QD	xxxxxx	xx/F	SBP (mmHg)	---	xxxx	ddMMMyyyy / hh:mm	x.x	90 to 140	
				400 mg QD	xxxx	ddMMMyyyy / hh:mm	x.x	90 to 140	L
					xxxx	ddMMMyyyy / hh:mm	x.x	90 to 140	
					xxxx	ddMMMyyyy / hh:mm	x.x	90 to 140	
				400 mg QD	xxxx	ddMMMyyyy / hh:mm	x.x	90 to 140	
					xxxx	ddMMMyyyy / hh:mm	x.x	90 to 140	H
					xxxx	ddMMMyyyy / hh:mm	x.x	90 to 140	
					xxxx	ddMMMyyyy / hh:mm	x.x	90 to 140	
					xxxx	ddMMMyyyy / hh:mm	x.x	90 to 140	
			...etc..						

F=Female; M=Male

Low or High results are highlighted in yellow.

Program: <program name (date, time)>, Path: <path>

Programming note: This listing excludes patients/parameters with normal results for all visits. Abnormal results and the Low/High flag will be highlighted in yellow.

Listing B.16.2.8.15 12-Lead ECG Results (Safety Population)

Starting Dose	Patient ID	Age/Gender	Current PRN Dose	Visit	Assessment #	Date / Time (ddMMMyyyy / hh:mm 24 hr)	Heart Rate (bpm)	QT Interval (msec)	PR Interval (msec)	RR Interval (msec)	QRS Duration (msec)	QTcF Interval (msec)	ECG Assessment	If Abnormal, details AE #, if abnormal CS
400 mg QD	xxxxx xx	xx/F	---	Screening		ddMMMyyyy	x.x	x.x	x.x	x.x	x.x	x.x	Normal	
			400 mg QD	xxxx	#1	ddMMMyyyy / hh:mm	x.x	x.x	x.x	x.x	x.x	x.x	Normal	
					#2	ddMMMyyyy / hh:mm	x.x	x.x	x.x	x.x	x.x	x.x	Normal	
					#3	ddMMMyyyy / hh:mm	x.x	x.x	x.x	x.x	x.x	x.x	Abn, NCS	
					Average/Worst finding		x.x	x.x	x.x	x.x	x.x	x.x	Normal	
					Additional	ddMMMyyyy / hh:mm	x.x	x.x	x.x	x.x	x.x	x.x	Normal	
					...etc... Average/Worst finding		x.x	x.x	x.x	x.x	x.x	x.x	Normal	
		xxxx	...etc..											

F=Female; M=Male

Abnormal NCS assessments are highlighted in yellow. Abnormal CS assessments are highlighted in pink.

Program: <program name (date, time)>, Path: <path>

Listing B.16.2.8.16 12-Lead ECG Results – Patient with Abnormal Results (Safety Population)

Cohort	Patient ID	Age/Gender	Current PRN Dose	Visit	Assessment #	Date / Time (ddMMMyyyy / hh:mm 24 hr)	Heart Rate (bpm)	QT Interval (msec)	PR Interval (msec)	RR Interval (msec)	QRS Duration (msec)	QTcF Interval (msec)	ECG Assessment	If Abnormal, details	AE #, if abnormal CS			
400 mg QD	xxxxx xx	xx/F	---	xxxx		ddMMMyyyy	x.x	x.x	x.x	x.x	x.x	x.x	Normal					
						400 mg QD	xxxx	#1	ddMMMyyyy / hh:mm	x.x	x.x	x.x	x.x	x.x	x.x	Normal		
								#2	ddMMMyyyy / hh:mm	x.x	x.x	x.x	x.x	x.x	x.x	Abn, NCS	xxx	x
								#3	ddMMMyyyy / hh:mm	x.x	x.x	x.x	x.x	x.x	x.x	Normal		
								Average/Worst finding		x.x	x.x	x.x	x.x	x.x	x.x	Abn, CS	xxx	x
								Additional	ddMMMyyyy / hh:mm	x.x	x.x	x.x	x.x	x.x	x.x	Normal		
								Additional	ddMMMyyyy / hh:mm	x.x	x.x	x.x	x.x	x.x	x.x	Normal		
			...etc..															

F=Female; M=Male

Abnormal NCS assessments are highlighted in yellow. Abnormal CS assessments are highlighted in pink.

Program: <program name (date, time)>, Path: <path>

Programming note: This listing excludes patients with normal assessments for all visits. Results for abnormal assessments will be highlighted in yellow.

Listing B.16.2.8.17 Physical Examination (Safety Population)

Startin g Dose	Patient ID	Age/ Gender	Body System	Current PRN Dose	Visit	Result	If abnormal, briefly describe
400 mg QD	xxxxxxx	xx/F	General Appearance	---	xxxx	Normal	
				400 mg QD	xxxx	Abnormal	xxxx
					xxxx	Not Done	
					xxxx	xxx	
					xxxx	Abnormal	xxx
				400 mg QD	xxxx	xxx	
					xxxx	xxx	
					xxxx	xxx	
					xxxx	xxx	
					xxxx	xxx	
		...etc..					

F=Female; M=Male

Abnormal assessments are highlighted in yellow

Program: <program name (date, time)>, Path: <path>

Listing B.16.2.8.18 Physical Examination – Patients with Abnormal Results (Safety Population)

Startin g Dose	Patient ID	Age/ Gender	Body System	Current PRN Dose	Visit	Exam Date and Time (ddMMMMyyyy hh:mm 24h)	Result	If abnormal, briefly describe
400 mg QD	xxxxxxx	xx/F	General Appearance	---	xxxx	dddMMMMyyyy hh:mm	Normal	
				400 mg QD	xxxx	xxxx	Abnormal	xxxx
					xxxx	xxxx	Not Done	
					xxxx	xxxx	xxx	
					xxxx	xxxx	Abnormal	xxx
				400 mg QD	xxxx	xxxx	xxx	
					xxxx	xxxx	xxx	
					xxxx	xxxx	xxx	
					xxxx	xxxx	xxx	
					xxxx	xxxx	xxx	
			...etc..					

F=Female; M=Male

Abnormal assessments are highlighted in yellow.

Program: <program name (date, time)>, Path: <path>

Programming note: This listing excludes patients with normal results for all body systems and all visits. Abnormal results will be highlighted in yellow.

Listing B.16.2.8.19 Pregnancy Test Results (Safety Population)

Starting Dose	Patient ID	Age/Gender	Current PRN Dose	Visit	Pregnancy sample collected?	Collection Date (ddMMMyyyy)	Collection Time (hh:mm 24h)	Pregnancy Lab Test	Result
400 mg QD	xxxxxxx	xx/F	400 mg QD	xxx	Yes	ddMMMyyyy	hh:mm	FSH	Negative
			400 mg QD	xxx	Yes	ddMMMyyyy	hh:mm	Serum Pregnancy	Negative
..etc..									

F=Female; M=Male

Program: <program name (date, time)>, Path: <path>

[figure not shown]
Listing B.16.2.8.20 Food Intake (Safety Population)

Starting Dose	Patient ID	Age/Gender	Current PRN Dose	Visit	Date of Food Intake (ddMMMyyyy)	Time of Food Intake (hh:mm 24h)	Food Intake
400 mg QD	xxxxxxx	xx/F	400 mg QD	xxx	ddMMMyyyyy	Hh:mm	xxxx
	..etc..						

F=Female; M=Male

Program: <program name (date, time)>, Path: <path>

[figure not shown]
Figure B.14.1.1.1 PDAI Score and PRN Dose Level By Study Day – Panel Plots (mITT Population)

DB Version: 06SEP2019.

Prednisone equivalent medication doses have been multiplied by 1000 and displayed using the 'PRN1008 Dose (mg/day)' axis. The true prednisone equivalent medication absolute minimum and maximum have been displayed on the graph for each patient.

Figure B.14.3.2.1 Scatter Plots of Peak TBL vs Peak ALT for Identification of Drug Induced Liver Injury (DILI) (Safety Population)

Patients are classified into different dose levels according to the dose they received at a given visit.
TBL = total bilirubin, ALT = alanine aminotransferase or SGPT, ULN = Upper Limit of Normal.
The maximum measurement value observed while on a given dose is defined as the peak value.
Program: <program name (date, time)>, Path: <path>

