9.8. Brain MRI

Brain MRI with macrocyclic contrast will be conducted on baseline and Day 15 visit for patients from French sites. Date of scan and results will be presented in a listing for the safety analysis population.

10. Pharmacokinetics/ Pharmacodynamics

The analyses of pharmacokinetics and pharmacodynamics (BTK occupancy) will be described and reported outside of the PRN1008-005 study report and attached as appendices.

ITT Analysis Population will be used for TFLs below.

The limit of quantifications for Anti-DSG 1, Anti-DSG 3 and Total Anti-DSG are 14, 9 and one or both of 14 or 9, respectively. Below the threshold is defined as negative, at or above these thresholds is defined as positive.

For Anti-DSG 1 and Anti-DSG 3 data, and a calculated variable of “total DSG” (Anti-DSG 3 and Anti-DSG 1 summed) summary tables presenting actual values and changes from baseline will be presented by visit overall and by maximum dose level. Missing values will not be imputed. This analysis will be performed only using Anti-DSG 1 and Anti-DSG 3 data above the limit of quantification, and for Total Anti-DSG, only use samples where at least one of Anti-DSG 1 or 3 is above the limit of quantification. Two exploratory DSG analyses will be performed:

- 1) CR status (without more than 0.5 mg/kg of CS prior to Week 13) yes/no at the Week 13 visit will be used to compare the change from baseline to Week 5 & 13 in Anti-DSG 1, Anti-DSG 3 data, and total DSG levels.
- 2) CDA status (without more than 0.5 mg/kg of CS and as defined for the primary endpoint) yes/no before Week 5 visit will be used to compare the change from baseline to Week 5 & 13 in Anti-DSG 1, Anti-DSG 3 data, and total DSG levels

All pharmacokinetics and pharmacodynamics data, including plasma concentrations of PRN1008, percentage BTK occupancy in PBMCs, and Anti-DSG 1-3 autoantibody levels (including quantified values below limit of quantification), will be presented in listings.

BTK occupancy data will also be described in a separate report.

11. Interim Analysis

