3.5.2 Missing data imputation

For AE data, missing causality will be imputed to “Related” and missing intensity grade will be imputed to “Grade 3 – Severe”.

Other missing data will not be imputed unless other specified.

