5.4.1.1 Subset Analyses

The robustness of the primary endpoint results will be explored by calculating the number and percent of patients meeting the primary efficacy endpoint overall (i.e. across all doses) within the following patient subsets:

- 1) Age (< 50 years, ≥ 50 years)
- 2) Gender
- 3) Total anti-desmoglein (DSG) antibody (≥ 100, < 100 units) at baseline.
- 4) Pemphigus History Type: Newly diagnosed (≤ 6 months from screening) vs. relapsed (> 6 months from screening)
- 5) Pemphigus anti-DSG Profile at baseline: Pemphigus Vulgaris (PV) vs. Pemphigus foliaceus (PF) vs. negative anti-DSG profile, defined as follows:
 - PV: anti-DSG3 positive with anti-DSG1 negative or anti-DSG3 positive with anti-DSG1 positive.
 - PF: anti-DSG1 positive only
 - Negative anti-DSG profile: neither detectable.
- 6) Pemphigus Severity: PDAI < 15 (mild-moderate) vs PDAI ≥ 15 (moderate-severe) at baseline If screening PDAI is not available use Week 1 Day 1 Pre-dose.

A sensitivity analysis using the Completer and PP populations will be provided for each subset analysis.

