5.4.2.5 Change from Baseline in Simple Nutritional Appetite Questionnaire (SNAQ) score

Simple Nutritional Appetite Questionnaire (SNAQ) contains 4 questions with numerical scores and is assessed at visits specified in the Schedule of assessments (Table 1). The SNAQ score will be calculated as the sum of scores from each question. The SNAQ score ranges from 4 to 20. If individual scores are missing, then the total score is set as missing.

Actual values and change from baseline in SNAQ score at each visit will be summarized by dose level and overall.

The SNAQ score will be presented in a listing by patient and visit.

5.4.2.1 *Change from Baseline and Percent Change from Baseline in Total Anti-DSG, Anti-DSG 1 and Anti-DSG 3*

The Anti-DSG 1 and Anti-DSG 3 results are measured at visits specified in the Schedule of assessments (Table 1). Total Anti-DSG is the sum of Anti-DSG 1 and Anti-DSG3, where at least one of Anti-DSG 1 or 3 is positive per Section 5.1.3, i.e. Anti-DSG 1 \geq 14 and/or Anti-DSG 3 \geq 9.

Actual result, change from baseline and percent change from baseline in Total Anti-DSG, positive Anti-DSG1, i.e. \geq 14, and positive Anti-DSG 3, i.e. \geq 9, at each visit will be summarized by dose level and overall. The same descriptive statistics will be produced by baseline Anti-DSG value (\geq 100 units vs. $<$ 100 unit).

The Total Anti-DSG, Anti-DSG 1 and Anti-DSG 3 values will be presented in a listing by patient and visit.

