Total Anti-DSG [3][4]			
< 100 unit	x (x.x)	x (x.x)	x (x.x)
≥ 100 unit	x (x.x)	x (x.x)	x (x.x)
PDAI total activity score [3]			
n	x	x	x
Mean (SD)	x.xx (x.xxx)	x.xx (x.xxx)	x.xx (x.xxx)
Median	x.xx	x.xx	x.xx
Min, Max	x.x, x.x	x.x, x.x	x.x, x.x
Pemphigus Severity [3]			
PDAI < 15 (mild-moderate)	x (x.x)	x (x.x)	x (x.x)
PDAI ≥ 15 (moderate-severe)	x (x.x)	x (x.x)	x (x.x)
PDAI Skin Activity > 0 n (%) [3]	x (x.x)	x (x.x)	x (x.x)
PDAI Scalp Activity > 0 n (%) [3]	x (x.x)	x (x.x)	x (x.x)
PDAI Mucous Membrane Activity > 0 n (%) [3]	x (x.x)	x (x.x)	x (x.x)
ABSIS Oral Involvement > 0 n (%) [3]	x (x.x)	x (x.x)	x (x.x)

[1] Based on date of first pemphigus reported in Medical History and date of screening

[2] Newly diagnosed is defined as subjects who were diagnosed at most 180 days prior to date of screening, otherwise the subject is relapsed.

[3] Result at Week 1 Day 1. If Week 1 Day 1 is missing, then the Screening result is used.

[4] Total Anti-DSG is the sum of Anti-DSG 1 and Anti-DSG3, where at least one of Anti-DSG 1 or 3 is positive, i.e. $\text{Anti-DSG 1} \geq 14$ and/or $\text{Anti-DSG 3} \geq 9$.

Percentages are based on the number of patients in each starting dose and overall.

Program: <program name (date, time)>, Path: <path>

Table B.14.1.4.1 Medical History (ITT Population)

Body System Code	Number of patients (%)		
	Starting Dose 400 mg QD (N = n)	Starting Dose 400 mg BID (N = n)	Overall (N = n)
Number of patients reporting any medical history	x (x.x)	x (x.x)	x (x.x)
Skin	x (x.x)	x (x.x)	x (x.x)
Head, Eyes, Ears, Nose, Throat	x (x.x)	x (x.x)	x (x.x)
Respiratory	x (x.x)	x (x.x)	x (x.x)
Cardiovascular	x (x.x)	x (x.x)	x (x.x)
Gastrointestinal	x (x.x)	x (x.x)	x (x.x)
Endocrine/Metabolic	x (x.x)	x (x.x)	x (x.x)
Genitourinary	x (x.x)	x (x.x)	x (x.x)
Neurological	x (x.x)	x (x.x)	x (x.x)
Blood/Lymphatic	x (x.x)	x (x.x)	x (x.x)
Musculoskeletal	x (x.x)	x (x.x)	x (x.x)
Hepatic	x (x.x)	x (x.x)	x (x.x)
Allergies	x (x.x)	x (x.x)	x (x.x)
Psychological/Psychiatric	x (x.x)	x (x.x)	x (x.x)
Other	x (x.x)	x (x.x)	x (x.x)

Percentages are based on the number of patients in each starting dose and overall.

If a medical history event of the same Body System Code is reported multiple times for a patient, it is counted only once.

Program: <program name (date, time)>, Path: <path>

Table B.14.1.5.1 Major Protocol Deviations (ITT Population)

Protocol Deviation Categories	Number of patients (%)		Overall (N = n)

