	400 mg QD (N = n)	400 mg BID (N = n)	600 mg BID (N = n)	Overall (N = n)
WEEK 1 DAY 1 (BASELINE)				
n	x	x	x	x
Mean (SD)	x.xx (x.xxx)	x.xx (x.xxx)	x.xx (x.xxx)	x.xx (x.xxx)
Median	x.xx	x.xx	x.xx	x.xx
Min, Max	x.x, x.x	x.x, x.x	x.x, x.x	x.x, x.x
WEEK 3 DAY 15				
n	x	x	x	x
Mean (SD)	x.xx (x.xxx)	x.xx (x.xxx)	x.xx (x.xxx)	x.xx (x.xxx)
Median	x.xx	x.xx	x.xx	x.xx
Min, Max	x.x, x.x	x.x, x.x	x.x, x.x	x.x, x.x
WEEK 3 DAY 15 – CHANGE FROM BASELINE				
n	x	x	x	x
Mean (SD)	x.xx (x.xxx)	x.xx (x.xxx)	x.xx (x.xxx)	x.xx (x.xxx)
Median	x.xx	x.xx	x.xx	x.xx
Min, Max	x.x, x.x	x.x, x.x	x.x, x.x	x.x, x.x
WEEK 3 DAY 15 – PERCENT CHANGE FROM BASELINE				
n	x	x	x	x
Mean (SD)	x.xx (x.xxx)	x.xx (x.xxx)	x.xx (x.xxx)	x.xx (x.xxx)
Median	x.xx	x.xx	x.xx	x.xx
Min, Max	x.x, x.x	x.x, x.x	x.x, x.x	x.x, x.x

Table B.14.2.2.49.1 Total Anti-DSG – Actual Values, Change and Percent Change from Baseline – Overall and by Baseline Value (mITT Population)

Group: All patients

	400 mg QD (N = n)	400 mg BID (N = n)	600 mg BID (N = n)	Overall (N = n)
WEEK 5 DAY 29				
...etc..				

Patients are classified into different dose levels according to the dose they received at each visit.

Total Anti-DSG is the sum of Anti-DSG 1 and Anti-DSG 3 if at least one of them is positive (Anti-DSG 1 \geq 14 and/or Anti-DSG 3 \geq 9).

Program: <program name (date, time)>, Path: <path>

Repeat for “Group: Baseline < 100” units and “Group: Baseline \geq 100 units”

Table B.14.2.2.49.2 Total Anti-DSG – Actual Values, Change and Percent Change from Baseline – Overall and by Baseline Value (Completer Population)

Table B.14.2.2.49.3 Total Anti-DSG – Actual Values, Change and Percent Change from Baseline – Overall and by Baseline Value (PP Population)

Table B.14.2.2.50.1 Anti-DSG 1 – Actual Values, Change and Percent Change from Baseline – Overall and by Baseline Value (mITT Population)

Footnote: Anti-DSG 1 data above the limit of quantification, i.e. \geq 14, are included.

Table B.14.2.2.50.2 Anti-DSG 1 – Actual Values, Change and Percent Change from Baseline – Overall and by Baseline Value (Completer Population)

Table B.14.2.2.50.3 Anti-DSG 1 – Actual Values, Change and Percent Change from Baseline – Overall and by Baseline Value (PP Population)

Table B.14.2.2.51.1 Anti-DSG 3 – Actual Values, Change and Percent Change from Baseline – Overall and by Baseline Value (mITT Population)

Footnote: Anti-DSG 3 data above the limit of quantification, i.e. \geq 9, are included.

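### Part B's definition of Total Anti-DSG, read literally, leaves patients negative on both assays in neither the <100 nor the ≥100 unit category at baseline and in the primary-endpoint subset

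*SAP*

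**What the plan says.** **Part B SAP.** Footnote [4] of Table B.14.1.3.1 (Disease History) reads "Total Anti-DSG is the sum of Anti-DSG 1 and Anti-DSG3, where at least one of Anti-DSG 1 or 3 is positive" and gives the cut-offs as DSG1 ≥14 and/or DSG3 ≥9. It is attached to the Total Anti-DSG row, whose only categories are <100 and ≥100 units. There is no row for missing or undefined values.

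The text on change in anti-DSG (the second section numbered 5.4.2.1, after 5.4.2.5) carries the same condition: "where at least one of Anti-DSG 1 or 3 is positive per Section 5.1.3". So does the footnote to Table B.14.2.2.49.1: "Total Anti-DSG is the sum of Anti-DSG 1 and Anti-DSG 3 if at least one of them is positive".

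Section 5.4.1.1, item 3, splits the primary endpoint by "Total anti-desmoglein (DSG) antibody" at 100 units at baseline. Neither that item nor the note under Tables B.14.2.1.4.x says where double-negative patients go. Item 5 of the same section has a category for them: "Negative anti-DSG profile: neither detectable". Section 5.1.3 and Table B.14.1.3.1 also count patients negative on both. Section 3.5.2 says "Other missing data will not be imputed unless other specified".

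**Part A SAP.** Section 10 defines total DSG as "Anti-DSG 3 and Anti-DSG 1 summed". It then restricts the Total Anti-DSG analysis to samples with at least one assay above its limit of quantification, using the same limits of 14 and 9. The notes to Tables 14.4.1.1, 14.4.2.1 and 14.4.2.2 repeat that restriction, and they set the total to missing if either component is missing. The baseline ≥100/<100 rows of Table 14.1.2.1, Section 8.2.11 item 3 and the programming note for Table 14.2.10.3.1 state no positivity condition.

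**The concern.** A condition suited to tracking antibody change over time has been written into the definition of the variable, and from there it governs a baseline classification for which it is not needed. The patients it removes are not a random few. They have the lowest titres in the study and would otherwise sit at the bottom of the <100 group.

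Three things are at stake, all within the descriptive subset and baseline tables:

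- The <100 group would consist only of seropositive patients with low titres, under a label that does not say so. If double-negative patients respond differently, the comparison of high with low titre shifts.
- The two baseline rows need not add to 100%, because percentages in Table B.14.1.3.1 are taken over all patients at each starting dose. No row explains the gap.
- Two programmers could produce different tables from the same SAP, one applying the only definition given and the other summing the two values for everyone.

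**Working it through.** The plan gives no figure on this point, so the check is a bound, a comparison of texts and an illustration.

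**1. Where a double-negative patient belongs.** Section 5.1.3 of the Part B SAP defines negative as DSG1 <14 and DSG3 <9. Hence

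DSG1 + DSG3 < 14 + 9 = 23 units < 100 units.

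The plain sum puts every such patient with both values recorded in the <100 category, with no borderline case.

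**2. Where the Part B definition puts that patient.** The total exists only if DSG1 ≥14 or DSG3 ≥9. Neither holds, so there is no total, and Section 3.5.2 does not fill it in. Table B.14.1.3.1 counts the patient in the row for negative on both assays and in neither Total Anti-DSG row. Applying the same definition to Section 5.4.1.1 item 3 gives the same result in Tables B.14.2.1.4.x.

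**3. Part A and Part B side by side.**

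| Use of Total Anti-DSG | Part A SAP | Part B SAP |
|---|---|---|
| Definition | Sum of the two | Sum, if at least one is positive |
| Actual-value and change summaries | Filter 14/9 applied | Filter 14/9 applied |
| Baseline <100/≥100 rows | No condition stated | Condition attached by footnote |
| Primary-endpoint subgroup at 100 units | No condition stated | Not restated; follows from the definition |

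The parts agree on the summaries. They differ in the baseline classification and whatever depends on it.

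**4. Size, as an illustration only.** Assumed: 25 patients (the planned number per Part), all with both assays recorded, 12 truly under 100 units, 6 of those 12 responders, and k double-negative patients among the 12. Leaving out k patients gives a denominator of 12 − k. The number of responders left lies between 6 − k (all omitted patients responded) and 6 (none did).

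| k | Lowest <100 rate | Highest <100 rate | Patients classified |
|---|---|---|---|
| 0 | 6/12 = 50% | 6/12 = 50% | 25 of 25 |
| 1 | 5/11 = 45.5% | 6/11 = 54.5% | 24 of 25 |
| 3 | 3/9 = 33.3% | 6/9 = 66.7% | 22 of 25 |
| 5 | 1/7 = 14.3% | 6/7 = 85.7% | 20 of 25 |

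For scale, the exact (Clopper-Pearson) 80% interval, the method planned for Part B, is 28.8% to 71.2% for 6/12. The shifts for k = 1 and k = 3 lie inside that interval; the extremes for k = 5 do not.

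**The case against.** The strongest reply is that the SAP never says these patients are excluded from the subset. Section 5.4.1.1 item 3 and the note under Tables B.14.2.1.4.x simply name the two titre groups, and a sensible programmer might count double-negatives as <100. This stands in part: exclusion from the subset is an inference from the definition. For the baseline rows it is more than that, because the footnote is attached to them.

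Second, the patients are not lost to the reader. Tables B.14.2.1.6.x report the primary endpoint for the negative profile, each subgroup table prints its number of patients, and Listing B.16.2.8.11 gives both assay values per patient. If the literal rule was followed, adding the negative-profile row to the <100 row recovers the full low-titre group. This also stands, but the reader would first have to work out which rule was followed.

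Third, comparing titre bands among seropositive patients only, with seronegative patients shown separately, is a defensible design. It is, but then the categories should be labelled that way, and Table B.14.1.3.1 does not do so.

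A reader might also infer two stronger points that the documents do not support:

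- **That Part A sums both values for everyone.** It does not. Section 10 applies the same 14/9 filter to actual values, changes and both exploratory comparisons. The absence of a condition in the Part A subgroup is silence in Section 8.2.11, not an express rule.
- **That the two Parts cannot be pooled on this variable.** Both SAPs list the component values, so one derivation can be applied to both. Pooling the subgroup tables as printed would require a check that the rules match.

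**Conclusion.** The point holds for the baseline categories as written and, by the same definition, for the titre subset of the primary endpoint. Part B's rule, followed literally, gives no category to patients who can only belong under 100 units, although the SAP plans to count such patients elsewhere.

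The consequence is limited. Part B performs no hypothesis testing, the subset is exploratory, and the overall primary proportion and its intervals do not change. If no patient is negative on both assays, nothing changes at all. The documents do not give that number, so no particular shift in the <100 rate can be claimed. The table above shows only that, with about 25 patients, one to five such patients could move the rate by about 5 to 36 percentage points in either direction under the stated assumptions. Nor do the documents show that double-negative patients respond differently, so a bias in a given direction cannot be asserted.

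**What to change.** State in the Part B SAP, in Section 5.4.1.1 item 3 and footnote [4] of Table B.14.1.3.1, that the baseline Total Anti-DSG categories use the plain sum of DSG1 and DSG3, so that patients negative on both count as <100 units. Apply the same rule to Tables B.14.2.1.4.x. Limit the condition that at least one assay be positive to the actual-value and change-from-baseline anti-DSG summaries (Tables B.14.2.2.49.x and the accompanying text).

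The cost is one sentence in the SAP, one changed footnote and one derived variable. No new data are needed, because both assay values are already collected and listed.
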